## Version 7.6

- Changed the time stamp to reflect first recorded time stamp patient was placed in a room to be seen by a physician or the first time AHF treatment is given, whichever comes first. The second part was added in case treatment is given by a triage physician.
- Clarified dosing of Lasix in protocol to a maximum dose of 200mg at any one time.
- Estimated urine output is acceptable.
- Clarifications to the protocol re: treatment per the usual care arm.
- Windows for follow up calls clarified.

## Version 7.8

1. Clarified the name of time of each scan (T24 changed to HD2) to ensure Image Nomenclature protocol and the Study protocol are the same
  - Dropped urine output guidance from treatment protocol
  - Extended the time window of the study to 6 hours post-enrollment, irrespective of patient location. However, this will NOT be a protocol violation if circumstances judged by the investigator do not allow for ED guided treatment to continue.
  - Editing and clarifications were also added

## Version 7.9

- Clarifies first dose of diuretic and difference between treatment arms

## Version 8.1

### Fixed discrepancy between DSMB charter and protocol regarding an interim analysis

The initial protocol used time from first ultrasound as the baseline assessment. However, per the initial revision listed above, we changed to time of first treatment. We did this b/c time of order of treatment and actual receipt of treatment were potentially large time windows. We wanted to avoid repeating US before any treatment was received. Unfortunately, this has led to more confusion as occasionally, patients receive treatment BEFORE the first US. How to account for this time has been challenging. As a result, we will revert to the original protocol; time of first US as the benchmark.

## LIST OF ABBREVIATIONS

AHF	Acute Heart Failure
USA	United States of America
HF	Heart Failure
ED	Emergency department
EP	Emergency Physician
LUS	Lung ultrasound
DAOOH	Days alive and out of hospital
NIV	Non-invasive ventilation (positive pressure ventilation)
NTG	Nitroglycerin
IV	Intravenous
SL	Sub-lingual
AKI	Acute Kidney Injury
WRF	Worsening renal function
WHF	Worsening heart failure
AE	Adverse event
SAE	Serious Adverse Event
SBP	Systolic Blood Pressure
Hgb	Hemoglobin
Hct	Hematocrit
IEC	Institutional Ethics Committee
IRB	Institutional Review Board
GCP	Good clinical practice
QC	Quality Control
CTSL	Clinical and Translational Sciences Lab at IU
IU	Indiana University
IWRS	Internet Web-based Randomization System

## STATEMENT OF COMPLIANCE

This study will be conducted in full accordance with the Good Clinical Practice: Consolidated Guideline approved by the International Conference on Harmonization (ICH) and any applicable national and local laws and regulations (e.g., Title 21 Code of Federal Regulations [21CFR] Parts 50, 54, 56, 312, and 314). Any episode of noncompliance will be documented.

The Investigators are responsible for performing the study in accordance with this protocol and the ICH and Good Clinical Practice (GCP) guidelines and for collecting, recording, and reporting the data accurately and properly. Agreement of each Investigator to conduct and administer this study in accordance with the protocol will be documented in separate study agreements with the sponsor and other forms as required by national authorities.

Each Investigator is responsible for ensuring the privacy, health, and welfare of the patients during and after the study and must ensure that trained personnel are immediately available in case of a medical emergency.

The Principal Investigator at each center has the overall responsibility for the conduct and administration of the study at that center and for contacts with study management, with the Independent Ethics Committee/Institutional Review Board (IEC/IRB), and with local authorities.

### PROTOCOL SUMMARY

**Title:** B-lines Lung Ultrasound Guided ED Management of Acute Heart Failure (BLUSHED-AHF)

**Précis:** Of the one million admissions for AHF in the US, approximately 80% are initially managed in the ED. Outcomes from AHF are poor: nearly 25% are dead or re-hospitalized within 30 days of discharge. The evidence base to treat AHF is limited. In fact, there are no pharmacologic therapies with Class I, Level A guideline recommendations. The acute

[figure not shown]
treatment of patients today is largely the same as 40 years ago. This proposal aims to build the evidence base for ED AHF care.

Using a multi-center, randomized controlled design, this pilot study will test whether a strategy of care – lung ultrasound (LUS) guided protocol-driven AHF therapy – outperforms usual care at reducing congestion in the ED setting.

Objectives:	
1. To determine whether a strategy of care – early LUS guided, protocol-driven ED AHF therapy – leads to more rapid resolution of congestion.
 
2. To demonstrate feasibility of recruitment and compliance with study protocol to inform future study design and enrollment projections

Endpoint	B-lines $\leq$ 15 at the conclusion of ED AHF management or maximum of 6 hours after enrollment, whichever comes first.
Population:	Emergency department (ED) AHF patients. All patients who meet inclusion and no exclusion criteria will be enrolled within 3 hours of presentation.
Phase:	2
Number of Sites enrolling participants:	Three sites (4 total hospitals). Projected sample size, n=130.
Description of Study Agent:	Strategy of Care: LUS guided protocol-driven ED AHF care vs. usual care.
Study Duration:	2 years. There will be three months of start up, and three months of study conclusion work. Enrollment will occur over 18 months, which equals 7.2 patients month. With 4 sites (2 at IU, 1 at Detroit, and 1 at Vanderbilt), this equals 1.8 patients/month.
Participant Duration:	90 days post discharge

## SCHEMATIC OF STUDY DESIGN

Figure 1: Trial Schematic

\*whichever comes first

^only if part of standard of care. Only NTpro and hsTnT will be drawn outside of standard of care

## 2 INTRODUCTION: BACKGROUND INFORMATION AND SCIENTIFIC RATIONALE

### 2.1 BACKGROUND INFORMATION

Over one million hospitalizations for AHF occur every year in the US. Within 30 days after hospitalization, over 25% of AHF patients will be dead or re-hospitalized. By one year after hospitalization, up to 67% of patients will be re-hospitalized and 36% will be dead. Worldwide, the costs of AHF exceed 100 billion annually. For patients aged 65 years and older, AHF is the most common and most expensive reason for hospitalization. Despite major reductions in morbidity and mortality for chronic HF, considerably less progress has been seen in AHF.

The emergency department (ED) initiates diagnosis and management for the vast majority of AHF patients. Nearly 80% of all admissions originate from the ED. Delays in diagnosis, misdiagnosis, and delayed or improper treatment are costly, associated with greater morbidity and mortality. One of the most expensive decisions in healthcare is made routinely from the ED; who gets hospitalized vs. discharged. Despite this crucial starting role, **ED AHF pharmacological management today is largely the same as 40 years ago.** In fact, guidelines state: *“the treatment of AHF remains largely opinion-based with little good evidence to guide therapy.”* Consensus statements from the American Heart Association as well as a working group from the NHLBI on ED AHF management further corroborate this lack of evidence: *“the evidence base on which this foundation of acute care is built is astonishingly thin.”* There remains a critical unmet need for evidence based ED AHF management.

Congestion is the primary reason why AHF patients present to the ED seeking medical care. Congestion is manifest by signs and symptoms of heart failure (HF) — for example, dyspnea, orthopnea, edema, and weight gain. Yet how to best assess, grade, and manage congestion is not well established. Only recently has the dosing of IV loop diuretics been studied; however patients were enrolled up to 24 hours after admission.

## 2.2 RATIONALE

### **Limitations of Current AHF Therapy**

There are currently no Class I, Level of Evidence A therapeutic guideline recommendations for AHF, highlighting the unmet need. In fact, therapeutic recommendations from the ACCF/AHA begin with hospital based management, highlighting the absence of ED based evidence. The last ED based guidelines were published in 2007 and have yet to be updated. We argue this lack of evidence leads to tremendous variation in ED care. Combined, this contributes to worse outcomes.

[figure not shown]
### **Targeting Congestion in AHF**

Freedom from congestion is associated with improved outcomes; yet many patients leave the hospital inadequately decongested. In fact, many patients leave the hospital without a pre-discharge assessment of congestion. We would argue many ED AHF patients are poorly assessed *prior* to hospitalization. The absence of robust, reliable methods to assess congestion is a primary reason why it is not assessed. A recent consensus statement published in 2010 highlights this fact: “...**no method to assess congestion prior to discharge has been validated.**” While physical exam is currently the cornerstone of congestion assessment, it lacks sensitivity and inter-rater reliability. The ED is the beginning of AHF management for >75% of admitted patients; delays in diagnosis, misdiagnosis, and resultant delays in management are associated with greater morbidity and mortality.

### **Lung Ultrasound**

For years, the lungs have been considered ‘off-limits’ to ultrasound: with aerated lungs, the ultrasound beam is reflected and scattered due to acoustic mismatch. However, in the setting of pulmonary congestion, extra vascular lung water (EVLW) can be directly visualized and quantitated. Lung ultrasound measurement of B-lines are an objective, semi-quantitative measure of extra vascular lung water (EVLW). B-lines are well-defined, vertical echogenic lines, originating from water-thickened interlobular septa. (Figure 1) They are a marker of congestion.

LUS improves diagnostic accuracy and is highly reproducible. Intra and inter-observer variability of B-line capture and summary have been reported as low as 5.1% and 7.4%, respectively. In a recent meta-analysis, LUS was the best test to affirm the diagnosis of AHF, more than natriuretic peptide (NP) (likelihood ratio positive for the diagnosis of AHF by LUS was 7.4 (95% CI 4.2-12.8) and LR negative 0.16, (95% CI 0.05-0.51)). This may reflect the additional value of LUS when patients have chronically elevated NP levels. Recent guideline and consensus statements also support the use of LUS for diagnosis.

Importantly, B-lines are a dynamic marker. In dialysis patients, B-lines decrease markedly pre/post dialysis. In AHF patients, B lines generally decrease throughout hospitalization. However, persistence of B-lines pre-discharge identifies patients at higher risk for worse outcomes. B-lines even outperformed BNP as a prognostic marker. Finally, serial measurement of B-lines are both easy to learn and perform. LUS is also low cost, and does not involve radiation. Computerized diagnostic aids have already been pilot tested with excellent results, demonstrating the ease of B-line scoring. Hand held machines perform as well as a standard ECHO platform or US machines. **The ease of LUS will facilitate its generalizability and dissemination.** Non-physicians may be future users of bedside LUS assessment, further supporting its generalizability.

We will also perform serial measures of LUS during hospitalization to further study its prognostic significance. By capturing treatment during hospitalization, we will better understand the trajectory of LUS B-line resolution, and determine whether future studies should continue to target LUS B-lines during inpatient therapy. We will also track physical exam, NTproBNP levels, eGFR, and hemoglobin/hematocrit levels as other measures of decongestion, to better understand the downstream impact of ED care. This will allow us to better discriminate the value of LUS compared to other measures.

**Prior Studies**

*Sonographic evidence of pulmonary congestion is associated with worse outcomes.*

We performed a single center pilot study of 44 patients who presented to the ED with dyspnea, evidence of B lines by LUS, and were admitted for AHF. Patients underwent LUS imaging during the ED (T0), within 24 hours (T1) and at discharge (Td). Vital status was determined by phone follow up within 90 days. Using a pre-specified cut-off of 15 B-lines as a marker of persistent pulmonary congestion, 50% of patients had evidence of EVLW at Td. The 28 sector scoring method was utilized. The average number of B-lines at T0 was 78±47 with a statistically significant reduction at T1 (44±33, p<.001) and Td (26±26, p<.05). (See Figure 2) Thirty-two patients (73%) were successfully contacted for follow-up.

[figure not shown]
[figure not shown]

Figure 3: Prognostic Value of LUS

Subjects at risk

— B-lines ≤15	60	60	60	60	59	59	59
- - - B-lines >15	40	37	33	31	31	28	27

During the follow-up period (median: 58 days, interquartile range: 44-82 days) 15 events occurred: 2 deaths and 12 all-cause re-hospitalizations. In the subset of patients who experienced events during follow-up, 93% were discharged with persistent presence of pulmonary congestion (> 15 B-lines) as measured by LUS.

Another pilot study of patients (n=100) admitted to a cardiology ward for shortness of breath and clinical concern for AHF demonstrated a statistically significant reduction in B lines at discharge (20+/- 23) vs. admission (48+/-48, p<.0001). At 6-month follow up, patients with ≥ 15 B-lines at discharge were significantly more likely to be re-hospitalized. (HR 11.7 (95% CI 1.3-106.6) (See Figure 3). In 27% of patients with >30 B-lines, no rales were reported by auscultation.

Additional work performed by one our study team members, [name], demonstrated a strong correlation between LUS B-lines and patients undergoing dialysis. This proof of concept supports B-lines as responsive to the removal of fluid. Coiro et.al. recently published a study of LUS performed throughout hospitalization, demonstrating the prognostic significance of residual congestion, as measured by B-lines.

Patients with  $\geq 30$  B lines had significantly worse combined outcome of all-cause mortality and HF re-hospitalizations at 90 days.

Importantly, these pilot studies also demonstrate the feasibility of performing LUS at the time of presentation and during hospitalization. **What has not been tested however, is the use of LUS to guide therapy.**

## 2.3 POTENTIAL RISKS AND BENEFITS

### 2.3.1 KNOWN POTENTIAL RISKS

Overview. Current ED AHF treatment involves the use of non-invasive ventilation (NIV), IV loop diuretics, and IV, SL, or topical vasodilators. Each of these are highlighted in guidelines. However, the level of evidence supporting these treatments is relatively weak, with the strongest evidence supporting the use of IV loop diuretics. The evidence is even weaker for ED AHF treatment; for example, the AHA/ACC guidelines begin with hospitalization, highlighting the lack of evidence for ED AHF care. Although the evidence is weak, these medications are the current standard of care for AHF. In patients receiving strategy-of-care, only therapies currently utilized will be employed. There are NO novel therapies or unapproved treatments.

Common Risks. The greatest risks are not necessarily different than those already associated with these therapies. However, the risk may or may not be increased due to use of these treatments in a guided protocol strategy. For IV loop diuretics, commonly encountered risks include potential acute kidney injury (AKI) and over diuresis leading to hypovolemia. Electrolyte abnormalities may also occur. Per routine standard of care at each of the sites, electrolytes are routinely checked during the initial 24-48 hours of treatment. These will be recorded. However, should no further electrolytes be measured after admission, a pre-discharge lab draw will be performed. While AKI may occur, more recent data suggests that failure to decongest is associated with greater risk for adverse outcomes than transient AKI. To add a margin of safety, only patients with an eGFR  $\geq 45$  will be enrolled. Finally, we will assess eGFR prior to discharge (if measured as part of standard of care) to better understand whether our proposed strategy-of-care is associated with worsening renal function. For nitrates, the greatest risk is hypotension. All patients will have IV access for fluids, if needed. Of note, the ESC guidelines allow for the potential use of IV nitrates in patients with a SBP  $> 110$ mmHg and only recommend avoiding them if the SBP is  $< 110$  mmHg. Another common side effect is headache, which will be treated with Tylenol or other non-narcotic analgesic medication. Use of NIV is both safe and effective. Greatest risks are those of aspiration in those with altered mental status. However, emergency physicians are well versed in the use of NIV as well as endotracheal intubation. No patients who are unable to protect their airway will be placed on NIV. Patients may also complain of claustrophobia or discomfort with the tight fitting mask. Attempts to adjust accordingly will be made. Anecdotally, patients feel significantly better and usually the improvement outweighs the discomfort. Other issues such as skin necrosis from long-term use of NIV does not apply to the short-term use of NIV.

An unknown risk is whether or not our treatment strategy is associated with myocardial injury. Thus, we will measure hsTnT at both baseline and pre-discharge to ascertain the incidence of myocardial injury.

Such measurements of hsTnT as potential electrolytes, eGFR, and pre-specified NTproBNP and Hgb/Hct will require additional blood draws, however, these will be limited in volume. No more than 40 cc total will be drawn for study purposes. While there are no known serious health risks related to the additional blood draw, there is the potential risk of pain, bruising, and rarely infection. Blood will be drawn by experienced technicians or research staff and whenever possible it will be obtained at a time when blood is being obtained for other tests that were ordered.

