### 6.1.2 DURATION OF THERAPY

Both arms will continue until 6 hours after randomization. 6 hours was chosen to avoid confounding by patients with overly long ED LOS. At minimum, patients should receive at least one round of treatment. The protocol continues even if patients reach the floor. However, if in the opinion of the investigator, the protocol should not be continued once on the hospital floor, this is allowed and should be marked on the case report form.

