## 7.2 LABORATORY PROCEDURES/EVALUATIONS

### 7.2.1 CLINICAL LABORATORY EVALUATIONS

Lab testing will be analyzed by the clinical lab at each respective institution for baseline chemistry and hemoglobin/hematocrit values. This reflects our pragmatic approach. If routine labs are performed clinically within 6 hours of the follow up time-point, these results will be used for study purposes (Table 2). If routine lab work is not drawn, the closest clinical lab draw will be recorded in the eCRF unless already recorded (i.e. the baseline value). NO labs, other than for NTproBNP and hsTnT will be drawn for study purposes. Samples will be stored and shipped to Indiana University at the Clinical and Translational Sciences Laboratory. At quarterly intervals, samples will be analyzed in our core lab, with expertise in clinical lab sampling.

All clinical laboratory test results outside of the reference range will be interpreted in the context of the patient underlying disease state by the Investigator using the following categories:

- abnormal but not a clinically-significant worsening
- abnormal and a clinically-significant worsening

A laboratory test result that has significantly worsened (according to medical judgment) compared with the baseline result will be recorded on the CRF as an adverse event and monitored. An adverse event includes a laboratory or diagnostic test abnormality (once confirmed by repeat testing as needed) that results in the temporary or permanent cessation of treatment, or requires medical treatment or further diagnostic work-up. The AE and SAE reporting period extends to day 5 of hospitalization or discharge, whichever comes first, unless otherwise specified.

A local laboratory will be utilized to analyze screening entry criteria.

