### 7.3.7 SCHEDULE OF EVENTS TABLE

Schedule of Events	Screening	Day 1 T00	Day 1 T02-04	Day 1 T06	Day 2-6 T24-D6	Day 7 or D/C*	30 & 90 day follow up	Quarterly
Informed consent (I/E)	X							
Medical History	X							
Medication history	X							
Clinical Assessment #		X	X	X	X	X		
Body Weight, height, Vital Signs	ED SOC	VS only	VS only	VS only	BW/VS only	BW/VS only		
Labs: Electrolytes, hematology, NP, eGFR, Troponin	ED SOC							
NT-proBNP / hsTroponin (for central lab processing)		X				X		
12-lead ECG	ED SOC							
CXR	ED SOC							
LUS B-lines 8 zone	X (LUS T00)		X	X	X	X		
LUS Guided AHF Management or Usual Care		X	X	X				
Lab draw: eGFR, Hgb/Hct ^		X				X*		
Prep and Storage of Samples		X				X		
eCRF/data collection/verification		X					X	

Assessment of AE/SAE's							X	
Phone follow-up Vital Status							X	
Batch shipment of samples								X
Subject payment		X					X	

SOC = standard of care, ED = Emergency Department, I/E = inclusion, exclusion, CV = cardiovascular, LUS = lung ultrasound, BW = body weight, NP = natriuretic peptide ^if collected as part of standard of care, will use that result. The last collected result will be used if not drawn on or close to discharge \*Day 7 or discharge, whichever comes first. #As documented by clinician during inpatient stay or per form for ED phase

Further detail regarding timing of assessments: [NOTE: given clinical circumstances (i.e. left the ER for a test, discussion with consultant, etc) – the SITE PI has final discretion to continue to image a patient before or after the allotted window. This time MUST be recorded in the eCRF]

- T00: initial LUS scan (in ED for screening and eligibility)
- T02: 2-4 hours after initial treatment (in ED) (+/- 30 minutes)
- T06: 2-4 hours after T02 or pre-ED discharge, whichever comes first (+/- 60 minutes)
- HD2: 24 hours after initial scan (Day 2) (+/- 6 hours)
- HD3: 48 hours after initial scan (Day 3) (+/- 8 hours)
- HD4: Day 4 (anytime during day)
- HD5: Day 5 (anytime during day)
- HD6: Day 6 (anytime during day)
- HD7: Day 7 (anytime during day)

\* NTproBNP/hsTnT blood draw. This should occur within 6 hours of randomization. Ideally, the blood draw should occur as soon as possible after randomization, preferably within 3 hours.

\*\* For vital signs during hospitalization. The nearest vital signs to the LUS exam will be captured.

^HD = Hospital day

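### The plan asks whether the strategy worsens renal function, but its only scheduled post-baseline eGFR is at day 7 or discharge, so an early fall that recovers is not counted by one rule in both arms

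*Combined protocol and SAP*

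**What the plan says.** Section 2.3.1 names acute kidney injury as a common risk of loop diuretics and leaves open whether a guided protocol raises it. It says recent data make failure to decongest a greater danger than transient kidney injury. It then asks whether the strategy is linked to a decline in renal function: "we will assess eGFR prior to discharge (if measured as part of standard of care) to better understand whether our proposed strategy-of-care". For the early period it names a different panel: "electrolytes are routinely checked during the initial 24-48 hours of treatment. These will be recorded".

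In the section 7.3.7 schedule, the row "Lab draw: eGFR, Hgb/Hct" is marked at T00 and at day 7 or discharge. It is blank at T02-04, T06 and days 2-6. Its footnote adds: "The last collected result will be used if not drawn on or close to discharge".

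Section 7.2.1 describes how laboratory values are obtained: "If routine labs are performed clinically within 6 hours of the follow up time-point, these results will be used for study purposes". Failing that, "the closest clinical lab draw will be recorded in the eCRF unless already recorded (i.e. the baseline value"). It allows no study draws except NT-proBNP and hsTnT. Section 6.1.2 fixes the length of protocol treatment: "Both arms will continue until 6 hours after randomization".

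An adverse event can also capture a renal change. Section 7.2.1 makes a judged deterioration an adverse event: "A laboratory test result that has significantly worsened (according to medical judgment) compared with the baseline result will be recorded on the CRF". It also counts an abnormality that stops treatment, needs treatment or needs further work-up. Section 8.1.1 adds new abnormalities, by the hospital's own laboratory standards, that lead to a new treatment.

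**The concern.** Protocol treatment ends at 6 hours, and the one scheduled follow-up eGFR may come days later, after inpatient care that the protocol does not control. A comparison of late values by arm addresses lasting change. It says little about an early fall that has since recovered, unless the patient's last value happens to be an early one.

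That early part matters because section 2.3.1 itself weighs transient kidney injury against failure to decongest. Weighing the two requires a count of the transient events in each arm. Section 2.3.2 makes sufficient safety the step to a later efficacy study, and section 3 says the pilot should supply what a definitive trial needs. If early falls are known only where a clinician judged, treated or investigated them, the next trial inherits a count that depends on behaviour in an unblinded setting.

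**Working it through.** The plan gives no renal figure to reproduce. The check sets the sections side by side and then works through assumed rates.

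**1. What eGFR data the plan yields**

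- Baseline: the ED standard-of-care panel at screening, and T00.
- Hours 2 to 6 and days 2 to 6: none scheduled. The 24-48 h labs in section 2.3.1 are electrolytes; creatinine and eGFR are not named.
- Late: day 7 or discharge, from a routine result within 6 hours, otherwise the closest draw (7.2.1) or the last collected (7.3.7 footnote). The time is not fixed: it could be day 1-2 in one patient and day 7 in another.
- Section 2.3.1 also mentions a fallback pre-discharge draw if electrolytes are not repeated after admission. Section 7.2.1 does not allow one. Either way it would not be an early value.
- Section 2.2 says eGFR will be tracked, but as a decongestion measure and with no added time-point.

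**2. How an early fall that recovers is counted**

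If the last value is late, the fall is seen only through the triggers in 7.2.1 (judged worsening, treatment cessation, treatment, further work-up) or 8.1.1 (abnormality leading to new treatment). None carries a numeric threshold. AKI and WRF are in the abbreviation list but are never defined numerically. Section 10.6.1 confirms that the trial is unblinded. Section 10.4.5 names hypotension and other safety events, with no renal variable, time or cut-off.

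**3. Illustration: how far the late difference can depart from the early one**

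Assumed, not in the documents: early falls in 10% (usual care) and 20% (LUS), a 10-point excess. Let rU and rL be the shares recovered by the last value.

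Late difference in points = 20 x (1 - rL) - 10 x (1 - rU).

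- rL = rU = 0.3: 14 - 7 = 7
- rL = rU = 0.7: 6 - 3 = 3

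With equal recovery, the late difference keeps the sign of the early one and is smaller.

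**4. Precision of an HD2 table**

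N = 130 (section 10.5) allocated 1:1 gives 65 per arm. If 80% have a panel (assumed), 0.8 x 65 = 52.

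Half-width of the 95% CI for a risk difference = 1.96 x sqrt[p1(1-p1)/n + p2(1-p2)/n]. For 10% vs 20% at n = 65: 1.96 x sqrt[(0.09 + 0.16)/65] = 0.122.

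| Assumed rates | n = 65 | n = 52 | Power, n = 65 |
|---|---|---|---|
| 5% vs 10% | 9.0 points | 10.1 points | 19% |
| 10% vs 20% | 12.2 points | 13.6 points | 35% |
| 15% vs 25% | 13.6 points | 15.3 points | 29% |

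Power is for the uncorrected chi-square test at two-sided 0.05, by exact enumeration.

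Half-width for a difference in mean eGFR change = 1.96 x SD x sqrt(2/n). Assumed SDs of 10, 15 and 20 mL/min/1.73m2 give 3.4, 5.2 and 6.9 at n = 65, and 3.8, 5.8 and 7.7 at n = 52.

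**The case against.** The case for leaving the plan alone has several parts.

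- **The measure matches the stated reasoning.** Section 2.3.1 treats transient kidney injury as the lesser risk and then chooses a pre-discharge value. This stands as a reason to keep discharge eGFR for persistent change. It does not supply the early count needed to weigh the two risks.
- **Adverse-event capture is broad.** Stopping a diuretic or working up a creatinine rise qualifies under 7.2.1, and 8.4.1 adds review of discharge summaries. This stands: early falls are not lost outright. But the triggers depend on clinicians, 8.2.3 lists acute renal failure as expected in this disease, and 8.4.1 investigates only non-exempt events without listing the exemptions.
- **Some late values are early.** Length of stay is not given, so the share of patients with no early value is unknown. This also stands.
- **Section 10.4.5 has generic methods** that could be applied to eGFR. True, but they cannot summarise a time-point that is not collected.
- **Renal safeguards exist:** exclusion below eGFR 45, a 200 mg cap on any single dose, and permission to hold uptitration. These reduce risk; they do not measure it.
- **The DSMB charter and the eCRF are not available.** The charter may hold renal rules, and the eCRF may already record sample times.
- **The HD2 value would still be clinician-ordered,** spread over 18 to 48 hours, and imprecise. This stands, and is why only description is proposed.

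A reader might infer that the late comparison could overstate or reverse the early one. The formula permits it: 70% recovery in usual care and 30% in LUS gives 14 - 3 = 11, and the opposite gives 6 - 7 = -1. The documents support no such opposed recovery rates. The -1 is 6% vs 7%, with a half-width of about 8.5 points at 65 per arm.

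**Conclusion.** The gap is real but limited. The plan asks about worsening renal function and has a reasonable measure of lasting change. It has no early renal comparison made by one rule in both arms. For patients whose last value is late, a fall that recovers depends on clinician-driven adverse-event triggers without a common threshold.

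Two stronger readings are not supported. One is that the design hides renal harm from the LUS arm. Early rates, recovery and length of stay by arm are not given, so neither direction nor size is known. The other is that the LUS arm receives four times the diuretic. The dosing example in 6.1.1 does imply 40 mg against 40 + 120 = 160 mg, but it concerns the first dose in one pre-treated patient. Usual-care patients may receive later algorithm doses (6.1, 6.1.1), and total day-1 dose by arm is not stated.

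The 7-to-3-point range and the interval widths rest wholly on assumed rates, SDs and panel availability. The primary endpoint is not affected. This is a cheap improvement to safety reporting, and the result can only be descriptive.

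**What to change.** 1. Add HD2 to the eGFR row in 7.3.7. Use the routine creatinine/eGFR nearest 24 h after T00 and within 6 hours of it; otherwise the first routine panel after that window, up to 48 h after T00. One value per patient, no study draw.
2. Record the date and time of both the HD2 and the late eGFR.
3. Add to 10.4.5, for example: *By arm, change in eGFR from T00 to HD2 (mean, SD, difference, 95% CI); number and proportion whose eGFR falls by at least 25%, with risk difference and 95% CI; number with a panel. Patients discharged before HD2 are shown separately, using their last panel. Descriptive, no formal test.* The 25% is an example; the investigators should choose the cut-off and fix it now.
4. Keep discharge eGFR for persistent change, and leave adverse-event reporting as it is.

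The cost is one laboratory field at a visit already scheduled, two time stamps, one table and some extra abstraction. Limits to state with the table: panel availability may differ by arm because clinicians order the panels; the routine 24-48 h panel is assumed to include creatinine; one panel can miss a later peak; and the intervals will be wide.
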